#### **7.1.2.1 Screening Period (Day -56 to Day -1)**

##### **7.1.2.1.1 Screening Visit 1 (Day -56 to Day -21)**

Patients will undergo Screening Visit 1 up to 56 days prior to the planned first day of study treatment.

Informed consent/assent must be obtained at the Screening Visit prior to performing any study procedures. After signing the informed consent form (ICF), patients will be evaluated for study eligibility.

Caregivers/patients will be instructed on the daily use of the Albireo electronic diary (eDiary). The eDiary will include observer reported outcome (ObsRO)/patient reported outcome (PRO) items for evaluation of itching (PRO), scratching (ObsRO), and sleep disturbance (PRO and ObsRO).

Daily recording of pruritus using the eDiary will be started to confirm the magnitude of baseline pruritus symptoms before randomization. The 14 consecutive days prior to randomization will be used for eligibility calculation of the diary entries. ObsRO in patients <18 years of age will be recorded by a caregiver. If possible, the same caregiver will complete the Albireo ObsRO items throughout the study.

Screening procedures and assessments are as follows:

- Obtain written informed consent

- Assess inclusion/exclusion criteria ([Section 7.2](#))
- Record demographics (age, full date of birth, gender, race, and ethnicity, as local regulations permit)
- Record any medications the patient has taken starting from Day 28 days before Screening Visit 1
- Medical and surgical history (date of diagnosis of ALGS, prior investigational medications for ALGS, historical LFT values [aspartate aminotransferase (AST), alanine aminotransferase (ALT) and bilirubin values obtained in the 2 years prior to screening if available should be entered into the electronic case report form (eCRF), any surgery performed including biliary diversion (if applicable), any other diagnosis, and historical liver biopsy data]. If a liver biopsy has been performed and the results are available, the results will be recorded in the eCRF. Record any symptoms of FSV deficiency. Medical and surgical history will be recorded through the timing of the first dose of study drug.
- Collect blood sample for ALGS genetic testing to determine eligibility if not available in the medical record. If a historical clinical genetic laboratory report for ALGS is available in the medical record, it is not required to collect a sample for genetic testing at this visit.
- Full physical examination ([Section 10.2.5](#))
- Vital signs ([Section 10.2.7](#))
- eDiary training and review of compliance requirements; caregivers and, if applicable, patients begin daily recording of pruritus using the eDiary ([Appendix 2](#))
- Clinical chemistry, hematology, and urinalysis ([Section 10.2.1](#))
- Serum bile acid ([Section 9.2.2](#))
- International normalized ratio (INR)
- Vitamins A and E
- 25-hydroxy vitamin D
- Serum pregnancy test for all females who have reached menarche. Please see [Appendix 6](#) for contraceptive requirements
- SAE monitoring

#### 7.1.2.1.2 Screening Visit 2 (Day -49 to Day -14)

A second Screening Visit will be performed. This visit is to confirm eDiary compliance and provide retraining if required. The two screening visits must be separated by at least 7 days, and Screening Visit 2 must occur at least 14 days prior to Study Day 1.

Screening procedures and assessments are as follows:

- Assess inclusion/exclusion criteria ([Section 7.2](#))
- Review concomitant medications
- Medical and surgical history will be recorded through the timing of the first dose of study drug
- Skin examination ([Section 10.2.5](#))
- Vital signs ([Section 10.2.7](#))
- Albireo ObsRO/PRO eDiary review of scores and compliance
- Clinical chemistry ([Section 10.2.1](#))
- Serum bile acid ([Section 9.2.2](#))
- Urine pregnancy test for females of who have reached menarche
- SAE monitoring and FSV deficiency questionnaire

#### **7.1.2.1.3 Repetition of Screening Assessments**

Screening assessments may be repeated to establish eligibility if the original assessment did not yield an interpretable result (e.g., quantity insufficient).

#### **7.1.2.1.4 Rescreening:**

Patients may be rescreened a total of 2 times.

#### **7.1.2.2 Treatment Period**

##### **7.1.2.2.1 Randomization (Study Day 1)**

Eligibility for randomization will be determined at Study Day 1 using the pruritus or scratching reports from the Albireo ObsRO/PRO instruments data in the 14 days before Study Day 1, clinical genetic confirmation of diagnosis, and the liver biochemistry evaluations from the previous screening visits.

At the randomization visit, the following assessments will be conducted:

- Review inclusion/exclusion criteria ([Section 7.2](#))
- Review concomitant medications
- Medical and surgical history will be recorded through the timing of the first dose of study drug.
- Full physical examination ([Section 10.2.5](#))
- Vital signs ([Section 10.2.7](#))
- Albireo ObsRO/PRO eDiary review for compliance and entrance criteria requirement (see Inclusion Criterion 2 and 5, [Section 7.2.1](#))
- Clinical chemistry and hematology ([Section 10.2.1](#))

- Serum bile acid ([Section 9.2.2](#))
- INR
- Autotaxin and plasma 7 $\alpha$ -hydroxy-4 cholesten-3 one concentration (p-C4) (samples will not be taken for patients  $\leq 10$  kg)
- Alfa-fetoprotein (AFP)
- Vitamins A and E
- 25-hydroxy vitamin D
- Liver ultrasound and elastography (where available) ([Section 10.2.6](#))
- Quality of life (QoL) questionnaire (Pediatric Quality of Life Inventory [PedsQL])
- Patient/caregiver/clinician complete the Global Impression of Symptoms (GIS) measures (PGIS/CaGIS/CGIS)
- Clinician assessment of xanthoma
- Urine pregnancy test for females who have reached menarche
- Study drug is dispensed and patients are instructed to administer daily from randomization (Study Day 1)
- SAE monitoring and FSV deficiency questionnaire. Non-serious AE monitoring begins after the first dose of study drug is taken

#### **7.1.2.2.2 Study Day 14 (Phone Call)**

A study site staff member will contact the patient/caregiver by telephone for monitoring of the following:

- Review concomitant medications
- Albireo ObsRO/PRO eDiary review for compliance
- AE monitoring and FSV deficiency questionnaire

#### **7.1.2.2.3 Week 4, 8, 16, and 20 Visits**

The following procedures and assessments will be performed:

- Review of concomitant medications
- Skin examination ([Section 10.2.5](#))
- Vital signs ([Section 10.2.7](#))
- Albireo ObsRO/PRO eDiary review for compliance
- Clinical chemistry ([Section 10.2.1](#))
- Hematology (at Week 4 visit only) ([Section 10.2.1](#))
- Serum bile acid ([Section 9.2.2](#))

- INR
- Odevixibat PK sample (at Week 4 and 20 only; samples will not be taken for patients  $\leq 10$  kg)
- Patient/caregiver/clinician complete the patient Global Impression of Change (GIC) measures (PGIC/CaGIC/CGIC) and GIS measures (PGIS/CaGIS/CGIS) (Week 4 visit only)
- Urine pregnancy test for females who have reached menarche
- AE monitoring and FSV deficiency questionnaire
- Evaluation of study drug compliance
- Study drug is dispensed

#### 7.1.2.2.4 Week 12 Visit

The following procedures and assessments will be performed:

- Review of concomitant medications
- Skin examination ([Section 10.2.5](#))
- Vital signs ([Section 10.2.7](#))
- Albireo ObsRO/PRO eDiary review for compliance
- Clinical chemistry, hematology, and urinalysis ([Section 10.2.1](#))
- Serum bile acid ([Section 9.2.2](#))
- INR
- Autotaxin and p-C4 (samples will not be taken for patients  $\leq 10$  kg)
- Vitamins A and E, and 25-hydroxy vitamin D
- QoL questionnaire (PedsQL)
- Patient/caregiver/clinician complete the PGIC/CaGIC/CGIC and PGIS/CaGIS/CGIS
- Clinician assessment of xanthoma
- Urine pregnancy test for females who have reached menarche
- AE monitoring and FSV deficiency questionnaire
- Evaluation of study drug compliance
- Study drug is dispensed

#### 7.1.2.2.5 Week 24/EOT Visit

For the Week 24/end of treatment (EOT), the patient has the option to continue in an open-label extension study, provided they meet eligibility criteria for that study.

For patients who permanently discontinue treatment early, during the treatment period, an EOT visit will be performed which includes the identical procedures that are performed at Week 24.

The following procedures and assessments will be performed:

- Review of concomitant medications
- Skin examination ([Section 10.2.5](#))
- Vital signs ([Section 10.2.7](#))
- Albireo ObsRO/PRO eDiary review for compliance
- Clinical chemistry, hematology, and urinalysis ([Section 10.2.1](#))
- Serum bile acid ([Section 9.2.2](#))
- INR
- Autotaxin and p-C4 (samples will not be taken for patients  $\leq 10$  kg)
- AFP
- Vitamins A and E, and 25-hydroxy vitamin D
- Odevixibat PK sample (samples will not be taken for patients  $\leq 10$  kg; EOT only)
- Liver ultrasound and elastography (where available) ([Section 10.2.6](#))
- QoL questionnaire (PedsQL)
- Patient/caregiver/clinician complete the PGIC/CaGIC/CGIC and PGIS/CaGIS/CGIS
- Clinician assessment of xanthoma
- Urine pregnancy test for females who have reached menarche
- AE monitoring and FSV deficiency questionnaire
- Evaluation of study drug compliance
- Exit interview

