	-56 to -21	-49 to -14									
Study Days	Clinic Visit 1	Clinic Visit 2	1	14 ± 3	28 ± 3	56 ± 3	84 ± 3	112 ± 3	140 ± 3	168 ± 3	196 ± 7
Clinic Visits			Clinic Visit 3	n/a	Clinic Visit 4	Clinic Visit 5	Clinic Visit 6	Clinic Visit 7	Clinic Visit 8	Clinic Visit 9	Clinic Visit 10
Phone Call				X							
Patient/Caregiver/ Clinician Global Impression of Symptoms			X		X		X			X	
Clinician assessment of xanthoma			X				X			X	
Pregnancy test m	X serum	X urine	X urine		X urine	X urine	X urine	X urine	X urine	X urine	X urine
Study drug dispensed n			X		X	X	X	X	X	X	
Adverse events o	All Adverse Events										
FSV Deficiency Questionnaire	X	X	X	X	X	X	X	X	X	X	X
Study drug compliance				X	X	X	X	X	X	X	X
eDiary compliance i		X	X	X	X	X	X	X	X	X	X
Exit Interview										X	

AFP: alpha-fetoprotein; eCRF: electronic case report form; eDiary: electronic diary; EOT: end of treatment; FSV: fat soluble vitamin; ICF: informed consent form; INR: international normalized ratio; p-C4: plasma 7α hydroxy 4-cholesten-3-one; PedsQL: Pediatric Quality of Life Inventory; PK: Pharmacokinetic; QoL: quality of life; SAE: serious adverse event.

a All assessments will be performed before dosing unless otherwise noted.

b The two screening visits must be separated by at least 7 days, and Screening Visit 2 must occur at least 14 days prior to Study Day 1.

c An EOT visit must be performed as soon as possible if study drug is prematurely discontinued. The EOT visit requires the same assessments as the Week 24 visit.

d The Safety Follow-up visit is required 28 days (±7) following the Week 24/EOT visit or the date of last dose for patients who prematurely discontinued study treatment. See Section 7.1.3 and Section 7.1.4 for when a Safety Follow-up visit is not required.

- e The ICF (and assent) must be signed before any study procedures are performed.
- f Past (within 28 days prior to Screening Visit 1) and current medication will be documented in the eCRF.
- g A full physical exam including skin exam will occur at Screening Visit 1 and Day 1. At all other clinic visits a skin exam and symptom-based physical exam will occur. Findings from the symptom-based physical exam will be documented as adverse events if appropriate.
- h Includes blood pressure, pulse, respiratory rate, temperature, height (or length depending on age), and body weight.

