#### **7.1.4 Early Discontinuation of Treatment During the Treatment Period**

Patients who prematurely discontinue study drug treatment during the treatment period will have an EOT visit as soon as possible after the decision is made to permanently discontinue study drug, and no later than their next scheduled visit. All efforts will be made to have patients continue to complete all scheduled study visits for assessments following completion of the EOT visit, as detailed in [Table 1](#). A safety follow-up visit is not required if patients continue to complete scheduled study visits after EOT. For patients who do not continue to attend scheduled study visits after EOT, a safety follow-up visit is not required if the EOT visit occurred more than 3 weeks after the last dose of study drug.

If study drug is permanently discontinued for any reason, the patient will be monitored weekly until the laboratory and clinical parameters have normalized/stabilized as clinically indicated. See [Section 10.1.3](#) regarding monitoring AEs and serious AEs (SAEs) after the patient's last study visit.

Permanent discontinuation of study drug may occur for any of the following reasons:

- Death
- Patient/caregiver estimation of intolerable symptoms
- Safety, behavior, or noncompliance with study procedures as determined by the investigator or Sponsor
- Treatment un-blinding
- An investigator's opinion that continuing the patient in the study is not appropriate. The investigator may permanently discontinue study drug at any time, if it is considered to be in the patient's best interest

If a patient permanently discontinues study drug and also withdraws consent or assent, no further assessments will be performed. Albireo may retain and continue to use any data and samples collected before such withdrawal of consent or assent.

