### **10.2 Laboratory Values/Vital Signs/Physical Examinations and Other Safety Assessments**

#### **10.2.1 Laboratory Assessments**

Samples will be collected for clinical chemistry, hematology, and urinalysis testing at the time points specified in [Table 1](#). The parameters assessed are presented in [Table 4](#).

At screening, alkaline phosphatase will be fractionated (liver, bone, and intestinal isoenzymes) for patients  $\geq$  age 18 at the time of enrollment. If alkaline phosphatase is elevated during the treatment period, isoenzymes can be re-measured to assist in evaluation of the alkaline phosphatase elevation.

Blood for AFP measurement will be drawn at randomization (Study Day 1) and Week 24/EOT visits. Blood for measurement of fat-soluble vitamin levels including vitamins A and E, and 25-hydroxy vitamin D will be drawn at Screening Visit 1, randomization (Study Day 1), Week 12, and Week 24/EOT visits. Blood for INR (surrogate for vitamin K) will be drawn at Screening Visit 1, randomization (Study Day 1), Week 4 to 24/EOT, and Safety Follow-up visits. Patients will fast (water intake only is permissible) for at least 4 hours prior to the collection of samples for vitamin A. Exceptions can be made for infants, <12 months of age, if unable to fast for the full 4 hours. If a patient has any vitamin level(s)

that are outside of the reference range, vitamin supplementation adjustments may be required. Target ranges and supplementation strategy guidelines can be found in [Appendix 5](#).

A serum pregnancy test will be performed at Screening Visit 1. A urine pregnancy test will be collected at all other visits for females who have reached menarche. If a urine pregnancy test is positive, a serum pregnancy test is to be performed to confirm the pregnancy. Study drug administration will be held pending the confirmatory results. If the serum pregnancy test is negative, the patient can resume dosing. If the serum pregnancy test is positive, the patient is to be discontinued (see [Section 10.2.9](#)).

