#### **10.2.6 Liver Ultrasound and Elastography**

Ultrasound of the liver and spleen will be performed at randomization (Study Day 1) and at Week 24/EOT. Liver size, echogenicity, and presence of masses/nodules will be recorded. Elastography will be performed as per institution standard practice where available.

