5.3 Appendix 3 Data Handling Conventions

Analysis windows for time points

The following analysis windows will decide how the scheduled and/or unscheduled visits will be used in the by-visit analyses of efficacy and safety variables. A measurement (scheduled or unscheduled) will be used if it is available and measurement date is within the analysis window.

After applying these time windows, if multiple assessments are associated to the same time point, the closest from the targeted study day will be used. In case of ties between observations located on different sides of the target day, the earlier assessment will be used. For laboratory parameters, central laboratory results will be used over local laboratory results if both are in a same analysis window.

Table 10.1 - Analysis visit windows (general)

Timing of assessment	Visit Name to display for Analysis	Targeted study day	Analysis window in study days / date of assessment
Screening	Baseline		<= -1
Randomization day 1	Baseline		1 (pre-dose)
Week 4	Week 4	28	Post-baseline to 42
Week 8	Week 8	56	43 to 70
Week 12	Week 12	84	71 to 98
Week 16	Week 16	112	99 to 126
Week 20	Week 20	140	127 to 154
Week 24	Week 24	168	155 to EOS ^a / 155 to EOS-1 ^b
4 Weeks Post Last Dose of Study Drug	Follow-up		EOS ^b

EOS=date of EOS assessment

^a For patients who rollover to Study A4250-015.

^b For patients who not rollover to Study A4250-015.

Table 10.2 - Analysis visit windows (GIC/GIS, PedsQL, xanthoma and selected lab tests)

Timing of assessment	Visit Name to display for Analysis	Targeted study day	Analysis window in study days / date of assessment
Screening	Baseline		<= -1
Randomization day 1	Baseline		1 (pre-dose)
Week 4	Week 4	28	Post-baseline to 56
Week 12	Week 12	84	57 to 126
Week 24	Week 24	168	127 to EOS ^a / 127 to EOS-1 ^b
4 Weeks Post Last Dose of Study Drug	Follow-up		EOS ^b

Note Selected lab tests include hematology, urinalysis, autotaxin, p-C4, Vitamins A & E and 25-hydroxy vitamin D.

EOS=date of EOS assessment

^a For patients who rollover to Study A4250-015.

^b For patients who not rollover to Study A4250-015.

Table 10.3 - Analysis visit windows (abdominal ultrasound and elastography, AFP)

Timing of assessment	Visit Name to display for Analysis	Targeted study day	Analysis window in study days / date of assessment
Screening	Baseline		<= -1
Randomization day 1	Baseline		1 (pre-dose)
Week 24	Week 24	168	71 to EOS ^a / 71 to EOS-1 ^b
4 Weeks Post Last Dose of Study Drug	Follow-up		EOS ^b

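### SAP Table 10.3 has no analysis window for liver ultrasound, elastography or AFP between the first dose and Day 70, so results from an early EOT visit in that period enter no by-visit safety summary

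*Protocol*

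**What the plan says.** **Protocol.** Section 7.1.2.2.5 states that for patients who permanently stop treatment early "an EOT visit will be performed which includes the identical procedures that are performed at Week 24". The procedures listed there include AFP, liver ultrasound and, where available, elastography. Footnote c of Table 1 agrees: "The EOT visit requires the same assessments as the Week 24 visit". These tests have very few scheduled time points. Section 10.2.6: "Ultrasound of the liver and spleen will be performed at randomization (Study Day 1) and at Week 24/EOT". Section 10.2.1: "Blood for AFP measurement will be drawn at randomization (Study Day 1) and Week 24/EOT visits". Section 7.1.4 wants the EOT visit as soon as possible after the decision to stop and "no later than their next scheduled visit". The Safety Follow-up visit in section 7.1.3 includes none of the three tests.

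**SAP.** Appendix 3 gives one rule, for efficacy and safety data alike, when results are analyzed by visit: "A measurement (scheduled or unscheduled) will be used if it is available and measurement date is within the analysis window". Table 10.3 is the window table for abdominal ultrasound, elastography and AFP. Its rows are:

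- Baseline: Day -1 or earlier, and Day 1 before dosing.
- Week 24: from Day 71 to the EOS date for patients who roll over to the extension, or to the day before EOS for those who do not.
- Follow-up: the EOS date, only for patients who do not roll over.

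**The concern.** The protocol requires a safety result at an early EOT visit, and the SAP then gives that result no place. An EOT visit on or before Day 70 lies after baseline and before the Week 24 row opens. Under the stated rule it is not used by visit.

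The omission is not random. Section 7.1.4 lists intolerable symptoms and safety among the reasons for permanent discontinuation, and the patients affected are those who stopped soonest. An early stopper who does not return at Week 24 has no other scheduled post-baseline ultrasound, elastography or AFP. Protocol section 10 counts liver ultrasound and elastography, as well as AFP, among the assessments in which safety trends are evaluated. A by-visit summary built on Table 10.3 would compare the arms without these patients.

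**Working it through.** No power or alpha figure is involved. The check assigns every possible EOT day to the windows and then gives a rough count.

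**1. Coverage of Day 2 to Day 168**

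| SAP table | First post-baseline window | Days with no window |
|---|---|---|
| 10.1 (general) | opens directly after baseline, to Day 42 | 0 |
| 10.2 (GIC/GIS, PedsQL, xanthoma, selected laboratory tests) | opens directly after baseline, to Day 56 | 0 |
| 10.3 (ultrasound, elastography, AFP) | opens at Day 71 | 70 - 2 + 1 = 69 |

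The 69 days in Table 10.3 are the same whether EOS falls 28 days after EOT or on Day 196. Day 1 after dosing is uncovered as well.

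**2. The exception.** If the EOT visit is itself the EOS assessment of a patient who does not roll over, the result goes to the Follow-up row. This can happen: sections 7.1.3 and 7.1.4 waive the Safety Follow-up visit if EOT falls more than 3 weeks after the last dose. The result then carries the label of a visit at which the protocol schedules none of these tests.

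**3. The EOT date decides, not the stop date.** The latest EOT day is the next scheduled visit plus its 3-day allowance.

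- Stop on Day 40: next visit Day 56, so EOT by Day 59. Always in the gap.
- Stop on Day 60: next visit Day 84, so EOT by Day 87. It may fall in the gap or in the Week 24 row.

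**4. How many patients.** Neither document gives a rate of early drug discontinuation. Assumptions: the 20% drop-out of protocol section 11.1 applies, stopping times are uniform over 168 days, and EOT is close to the stop.

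- Early stoppers: 45 × 0.20 = 9.
- EOT on Days 2 to 70: 9 × 69/168 = 3.7, which is 3.7/45 = 8% of the trial.
- If instead every patient who stops from Day 56 on has EOT after Day 70, only stops on Days 2 to 55 count: 9 × 54/168 = 2.9.
- Drop-outs who withdraw consent have no EOT scan, and early stoppers who attend Week 24 have a later result inside the window. The number left with no by-visit result can therefore be as low as 0.

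**5. Other routes into the output**

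| Test | By-visit row, EOT on Days 2 to 70 | Last-visit change | Highest/lowest shift | Listing |
|---|---|---|---|---|
| AFP | none | yes (SAP 4.8.2.1) | yes (SAP 4.8.2.1) | yes (Protocol 11.2.2.8) |
| Ultrasound, elastography | none | none described | none described | yes (Protocol 11.2.2.8) |

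**The case against.** Several counter-arguments have force.

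- **The data are not lost.** A reader might infer that early scans disappear. They do not: protocol section 11.2.2.8 promises per-patient listings of all safety parameters, and SAP section 4.1 bases its listings on all randomized patients. The windows govern by-visit analyses only. This stands, although a listing does not compare the arms.
- **No imaging table is described.** SAP section 4.8 names abdominal ultrasound as an assessment and omits elastography. Section 4.8.2 covers only laboratory variables and vital signs, and the table templates are in a separate document. It is tempting to say that the imaging summaries will be biased toward patients who tolerated treatment. The documents support less than that: a window table implies a by-visit display, but its content, and any last-assessment display beside it, cannot be seen.
- **Not every early stopper is affected.** Elastography depends on availability, and assessments end when consent is withdrawn. Section 7.1.4 asks for early stoppers to be kept on scheduled visits, so a Week 24 result may still exist. It would also be wrong to call the EOT scan the only liver imaging on study, since all patients are scheduled for one on Day 1.
- **Early liver harm is captured elsewhere.** Adverse event tables, laboratory shift tables, the liver-monitoring listing and hepatic adjudication do not depend on Table 10.3.
- **Keeping a very early scan out of a Week 24 row is defensible.** This is fair as an argument about the label. It does not explain the missing row. Table 10.3 already counts Day 71 as Week 24, which is 168 - 71 = 97 days before the target day, whereas Table 10.1 opens Week 24 at Day 155. The SAP gives no reason for Day 71 and does not say where earlier results are to be summarized.

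**Conclusion.** The gap is real and specific to Table 10.3. AFP, ultrasound and elastography results from an EOT visit on or before Day 70 have no analysis visit, or are labelled follow-up if that visit is also the EOS assessment of a patient who does not roll over. For AFP the loss is partial. For imaging, only the listing remains among the outputs that the documents describe.

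The effect is small. Safety analyses are descriptive, and no primary or key secondary result changes. The size is 0 to about 4 of 45 patients. That range borrows the planned drop-out rate as a rate of early discontinuation and assumes uniform stopping times, for which the documents give no source; stops clustered early would raise the count. The existence of the gap needs none of these assumptions, because it follows from the two documents read together. It is worth closing because what is left out is a protocol-required safety result, selectively from those who stopped soonest.

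**What to change.** In SAP Appendix 3, Table 10.3:

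1. Keep the Week 24 row as it is and add a separate row, Early EOT, running from post-baseline to Day 70. The row has no target day, so name the EOT assessment as the one used if there are several.
2. Add a summary of the last post-baseline assessment for ultrasound and elastography, matching the last-visit summary that laboratory variables already have.
3. State that an EOT or Week 24 assessment keeps that label even when it is also the EOS assessment.

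Moving the start of the Week 24 window back to post-baseline would be simpler but worse. It would pool a scan from the first weeks with Day 168 scans under one label. It could also displace a genuine Week 24 scan: section 7.1.4 waives the Safety Follow-up for early stoppers who continue scheduled visits, so in a patient who does not roll over, the Week 24 visit may be the EOS assessment. The limit of EOS minus one day would then send that scan to follow-up and let the early EOT scan fill the Week 24 row.

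The cost is one extra, sparse row in descriptive tables, one added imaging summary and one sentence on labels. No new data are needed.
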